9.2.3. Sample Size Re-estimation or Adjustment

At the time of this protocol amendment, the study was fully enrolled, and as such no sample size re-estimation was performed.

9.3. Data Analysis Considerations

9.3.1. Analysis Populations

The primary population for analyses of MACE and other time to event outcomes will be the All Randomized (ITT) Population. Subjects will be analyzed according to the treatment to which they were randomized.

The primary population for the Hgb efficacy analyses will also be the ITT Population. A supportive analysis of the primary efficacy endpoint will be performed in a Per-Protocol (PP) Population defined as all ITT subjects who are not major protocol violators. Details will be defined in the RAP and subjects analyzed according to the treatment received.

The primary population for safety will be based on all randomized subjects who receive at least one dose of randomized treatment. Subjects will be analyzed according to the treatment received.

Additional populations may be defined in the RAP, including sub-study populations.

9.4. Key Elements of Analysis Plan

9.4.1. Primary Analyses

9.4.1.1. Primary CV Safety Analysis (co-primary)

MACE: The co-primary cardiovascular safety analysis is to assess the comparative treatment effect for time to first occurrence of adjudicated MACE in all randomized subjects. Time to the first occurrence of a primary endpoint event will be computed as (event date – randomization date) +1. Subjects who do not have the event during the trial period will be censored in the analysis, with details provided in the RAP. The statistical model is a Cox Proportional Hazards regression model, adjusting for treatment and the prognostic randomization stratification factors (dialysis type and region), to estimate the hazard ratio, two-sided 95% CI and one-sided p-value for the statistical non-inferiority test. Non-inferiority will be established if the upper limit of the two-sided 95% CI is less than the margin of 1.25. Cumulative time from randomization to first event or end of trial will be evaluated using Kaplan-Meier methodology and displayed graphically. Treatment comparisons from the Cox regression model will be presented as hazard ratios and two-sided 95% CIs and displayed on forest plots. The validity of the proportional hazards assumption will be assessed. All adjudicated events will be used for the primary analysis and concordance between investigator reported and adjudicated events will be summarized.

Sensitivity and Supportive Analyses: A sensitivity analysis will be performed to address potential effects of drop outs and to evaluate the robustness of the co-primary

MACE analysis. A sensitivity “tipping point” analysis utilizing multiple imputation for randomized subjects who have withdrawn from the study will be performed, as well as a supportive “on-drug” analysis to evaluate the comparative treatment effect during the time that subjects remain on randomized treatment (plus a window of 28 days). Full details will be provided in the RAP.

In addition, analyses will be performed for each component of MACE (all-cause mortality, MI and stroke) to understand individual contributions to the overall MACE result and to assess component directional consistency. These analyses will not be multiplicity adjusted. Further subgroup and covariate adjusted analyses of specific clinical interest are detailed in Section 9.4.4 and the RAP.

9.4.1.2. Primary Efficacy Analysis (co-primary)

Mean change in Hgb between baseline and the EP (Weeks 28 to 52): The primary efficacy estimand is the effect of daprodustat relative to rhEPO on the change in Hgb from baseline to the average of all values in the EP, regardless of adherence to treatment including interruptions and discontinuation, the use of non-randomized ESA medication for any reason including rescue therapy, or the use of blood transfusions, in subjects on dialysis currently treated with an ESA with anemia secondary to CKD and assuming subjects do not die before the end of the EP. The analysis will use an ANCOVA model. For each subject, baseline Hgb will be the value obtained on Day 1, prior to taking randomized treatment, and Hgb during EP will be determined by calculating the mean of all available and imputed Hgb values between Weeks 28 to 52 inclusive regardless of adherence to randomized treatment. The ANCOVA model will include prognostic randomization stratification factors (dialysis type and region), baseline hemoglobin and treatment. It will provide a point estimate and two-sided 95% CI for the treatment effect together with the one-sided non-inferiority test p-value. Non-inferiority will be established if the lower limit of the two-sided 95% CI is greater than the margin of -0.75 g/dL. Imputation will be used for missing Hgb data; further details will be provided in the RAP.

Sensitivity and Supportive Analyses: Sensitivity analyses for the primary estimand will include a multiple imputation-based “tipping point” analysis where assumptions are adjusted until non-inferiority is lost by imputing data for subjects who did not fully complete the EP. A supportive analysis will evaluate efficacy in those subjects who adhere to randomized treatment, defined as ITT subjects with at least one on-treatment Hgb during the EP (this approach corresponds to evaluating an efficacy estimand). A supportive “tipping point” analysis as that described above for the primary analysis will be performed for this “on-drug” analysis. In addition, a per-protocol supportive analysis will estimate the treatment effect in subjects who strongly adhere to the protocol, and supportive analyses to explore a shorter EP (Weeks 28 to 36) will be performed for the co-primary effectiveness estimand and “on-drug” efficacy estimand. Full details of all sensitivity and supportive analyses will be provided in the RAP.

9.4.2. Secondary Analyses

9.4.2.1. Principal Secondary Analyses

Conditional on the co-primary endpoints achieving at least non-inferiority at the one-sided 2.5% level, statistical testing will progress to superiority for MACE and the principal secondary endpoints. The hypotheses to be tested for these endpoints are as follows:

- **Null:** daprodustat is not superior to rhEPO (i.e. the hazard ratio is greater than or equal to 1.0 for time-to-event endpoints, or the mean difference is greater than or equal to 0 for continuous endpoints)
- **Alternative:** daprodustat is superior to rhEPO (i.e. the hazard ratio is less than 1.0 for time-to-event endpoints, or the mean difference is less than to 0 for continuous endpoints)

These tests will be multiplicity adjusted based on a family-wise Type I error rate set at the one-sided 2.5% level, see Section 9.4.3 for further details.

For “time to event” endpoints: The statistical modeling approach described for MACE in Section 9.4.1.1 will be repeated for the adjudicated composite endpoints of:

- MACE or a thromboembolic event (vascular access thrombosis, symptomatic deep vein thrombosis or symptomatic pulmonary embolism).
- MACE or hospitalization for HF.

For the average monthly IV iron dose up to Week 52 endpoint: IV iron use for all subjects will be recorded in the eCRF and the average monthly IV iron dose up to week 52 will be calculated. An ANCOVA model will be used to compare the difference in this average monthly IV iron dose per subject between arms, including factors for baseline dose, treatment and the prognostic randomization stratification factors.

Additional secondary endpoints are listed in [Appendix 2](#). All analyses of secondary endpoints are of exploratory nature, summary statistics and nominal one-sided p-values will be used for any treatment comparisons.

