3. OBJECTIVE(S) AND ENDPOINT(S)

Objectives	Endpoints
Co-primary (tested in parallel for non-inferiority)	

 To compare daprodustat to rhEPO for CV safety (non-inferiority) 	
 Time to first occurrence of adjudicated MACE (composite of all-cause mortality, non-fatal MI and non-fatal stroke)

 To compare daprodustat to rhEPO for Hgb efficacy(non-inferiority) 	
 Mean change in Hgb between baseline and EP (mean over Weeks 28 to 52)
Principal Secondary (tested for superiority, adjusted for multiplicity)	

 To compare daprodustat to rhEPO on CV safety endpoints 	
 Time to first occurrence of adjudicated 
 MACE MACE or a thromboembolic event (vascular access thrombosis, symptomatic deep vein thrombosis or symptomatic pulmonary embolism) MACE or a hospitalization for heart failure (HF)

 To compare daprodustat to rhEPO on the use of intravenous (IV) iron 	
 Average monthly IV iron dose (mg)/subject to Week 52
Safety	

 To compare the safety and tolerability of daprodustat to rhEPO 	
 Incidence and severity of AEs and serious adverse events (SAEs) including AEs of special interest¹ Reasons for discontinuation of randomized treatment Absolute values and changes from baseline in laboratory parameters, BP and heart rate (HR)

1. Defined as thrombosis and/or tissue ischemia secondary to excessive erythropoiesis; worsening of hypertension;cardiomyopathy; pulmonary artery hypertension; cancer-related mortality and tumor progression and recurrence; esophageal and gastric erosions; proliferative retinopathy, macular edema, choroidal neovascularization; and exacerbation of rheumatoid arthritis

Additional secondary and exploratory objectives/endpoints are listed in [Appendix 2](#).

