4. STUDY DESIGN

4.1. Overall Design

- This is a randomized, open-label (sponsor blind), active-controlled, parallel-group, multi-center, event-driven study in dialysis subjects with anemia associated with CKD who are currently treated with ESAs².

[figure not shown]
² ESAs refer to any rhEPO or methoxy PEG-epoetin beta.

- This study will comprise four study periods (Figure 1): a 4-week screening period, a 4-week placebo run-in period, a treatment period and a follow-up period. Prior ESA therapy continues during the screening and run-in periods.
- The treatment period consists of :
 1. The stabilization period, defined as the period from Day 1 to Week 28 during which randomized treatment will be dose titrated to achieve the appropriate Hgb target
 2. The maintenance period, defined as the period from the end of the stabilization period (Week 28) to the end of treatment (variable per subject), to assess long term safety and efficacy.
 - The efficacy evaluation period (EP) is defined as the period from Week 28 to Week 52 during which Hgb efficacy will primarily be assessed.
- The total duration of the study is dependent upon the accumulation of 664 adjudicated first MACE (i.e., it is event-driven) unless review of interim data by the IDMC recommends bringing the study to an earlier close.
- All subjects will remain in the study (including subjects receiving kidney transplant), regardless of whether they continue with randomized treatment (unless consent for any further follow up is withdrawn), until the target number of first adjudicated MACE has occurred. At that point, the sponsor will notify investigators to have subjects come in for an End of Study visit within a pre-defined time period.
- The end of the study will occur after the accumulation of 664 adjudicated first MACE and the last subject has completed their last required study visit (Section 7.1).
- Subjects will be stratified by dialysis type [HD* or PD], by region (see Appendix 3), and by participation in the ABPM sub-study. Dialysis type and region are stratification factors considered to be potentially prognostically important, i.e., predictive of study endpoints while participation in the ABPM sub-study is an administrative stratification factor intended solely to ensure a similar number of sub-study subjects in each of the two randomized groups.

* HD group also includes hemodiafiltration (HDF) or hemofiltration (HF).

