- Following stratification, subjects will be randomized 1:1 to receive oral daprodustat or rhEPO (IV epoetin alfa for HD subjects and SC darbepoetin alfa for PD subjects). A central randomization approach will be used to protect against potential selection bias due to the open-label design. The sponsor is blinded to treatment assignment in the main study and ABPM sub-study.
- Both treatment arms (daprodustat and rhEPO) will follow a protocol-specified randomized treatment dose adjustment algorithm to achieve and/or maintain Hgb within the target range of 10-11 g/dL (Section 6.3.3). Dose changes will be made programmatically by the Interactive Response Technology (IRT) system for both randomized treatment arms.

- To ensure subjects remain iron replete and to minimize the potential for iron overload during the study, the investigator will follow the iron management criteria (Section 6.11.1) from randomization through the end of the study treatment period.
- A rescue algorithm is provided to minimize subjects having an inadequate response to the treatment for their anemia for an extended period of time and to enable consistency in the application of rescue therapy across the study (Section 6.12).
- An overview of the study design is provided in Figure 1.

Figure 1 Study Schematic

- This study will include the following sub-studies:
 - ABPM sub-study ([Appendix 12](#))
 - Pharmacokinetic (PK) sub-study ([Appendix 13](#))
- An external independent Clinical Events Committee will conduct blinded adjudication of all events reported during this study that may meet the definition of the co-primary safety endpoint of MACE and additional endpoints as outlined in Section 7.4.1 and Section 10.8.2.
- An external IDMC will monitor the safety and efficacy data from the study (Section 10.8.1).

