4.2. Type and Number of Subjects

- This study will randomize approximately 3000 dialysis subjects (1500 per treatment arm) with anemia associated with CKD currently receiving an ESA and with a baseline HemoCue Hgb 8-11.5 g/dL (Section 5.1).
- Subjects may be on HD or PD. PD subjects will be restricted to no more than 15% of the overall study population.

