6.11.1. Iron Management Criteria

Subjects must remain iron replete throughout the study. The investigator will follow the iron management criteria from randomization (Day 1) through the end of the study treatment period for subjects receiving randomized treatment.

Iron therapy will be administered if ferritin is ≤ 100 ng/mL and/or TSAT is $\leq 20\%$. The investigator should choose the route of administration and dose of iron based on the subject's iron status and local clinical practice.

All iron (excluding multivitamins) must be stopped and cannot be administered if;

- Ferritin > 800 ng/mL and TSAT $> 20\%$, or
- TSAT $> 40\%$

Investigators should be guided by local/regional guidelines and may stop administration of iron at a lower ferritin or TSAT level as long as subjects are maintained at a ferritin > 100 ng/mL and TSAT $> 20\%$.

The Steering Committee (Section 10.8.4) will monitor blinded subject iron data in an ongoing fashion to ensure compliance.

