7.1. Time and Events Table

Table 7 Schedule of Assessments Year 1 to End of Study

Protocol activity (visits ± 1 week, except Weeks 2 and 4 which are ± 3 days) All assessments pre-dialysis unless otherwise specified (Note: All visit timings are relative to Day 1)	Day 1 through Week 52							
	Screen Week -8	Run-in Week -4	Day 1 ¹³	Week 2	Full study visit Week 4, 16, 28, 40	Abbreviated study visit Week 8, 12, 20, 24, 32, 36, 44, 48	Week 52	Unscheduled ¹⁰
Informed consent (main study)	X ²²							
IRT system transaction ¹⁷	X	X	X	X	X	X	X	X
Subject reminder, inform site staff of changes in health ¹			X				X	
Check/confirm entry criteria	X		X					
History: medical, hospitalization, transfusion demography, height	X							
Weight (pre- and post-dialysis for in-center HD subjects; between treatments for HHD; at study visits per standard of care for PD) and EDW	X	X	X	X	X	X	X	X
SBP/DBP, HR (pre- and post-dialysis for in-center HD subjects; between treatments for HHD; at study visits per standard of care for PD) (single readings unless otherwise indicated)	X	X	X (triplicate)	X	X	X	X (triplicate)	X
Kt/V _{urea} ¹⁸			X		X		X	
ECG ²			X ²				X	
Ultrasound of kidneys and adrenal glands		X ¹⁶						
Placebo run-in or randomized treatment dispensing (start administration on date treatment dispensed) ¹⁹		X (placebo)	X	X ⁹	X	X	X	X ⁹
Placebo run-in or randomized treatment compliance ¹⁹			X (placebo)	X ¹¹	X	X	X	X ¹¹
Iron therapy, transfusions ³	X	X	X	X	X	X	X	X
Rescue medication(s) for Initial Intervention ^{3,4}					X	X	X	
Females only: estradiol and FSH (if required)	X							
FRP only: Serum pregnancy test ^{5,20}		X	X		X		X	
HemoCue Hgb	X	X	X	X	X	X	X	X
Hematology ⁶	X	X	X		X	Hgb only	X	X
Clinical chemistry ⁶	X		X		X		X	X

Protocol activity (visits ± 1 week, except Weeks 2 and 4 which are ± 3 days) All assessments pre-dialysis unless otherwise specified (Note: All visit timings are relative to Day 1)			Day 1 through Week 52					
	Screen Week -8	Run-in Week -4	Day 1 ¹³	Week 2	Full study visit Week 4, 16, 28, 40	Abbreviated study visit Week 8, 12, 20, 24, 32, 36, 44, 48	Week 52	Unscheduled ¹⁰
Ferritin, total iron, UIBC ⁶	X		X		X		X	
Hepcidin			X		X		X	
HbA1c ⁷ , lipids (non-fasting)			X				X	
hsCRP, iPTH			X		Wk 28		X	
Storage biomarkers ²¹			X		Wk 28		X	
Hospitalization ³ , kidney transplant ³				X	X	X	X	X
Non-serious AEs, SAEs, AEs of special interest, clinical events	X ⁸	X	X	X	X	X	X	X
Review concomitant medications	X	X	X	X	X	X	X	X

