9.4.3. Multiplicity Strategy

The multiplicity strategy for this trial will use a combination of a gatekeeper approach on the co-primary endpoints, followed by a closed-test multiplicity procedure wrapped around the family of superiority hypotheses consisting of MACE and the principal secondary endpoints.

Figure 2 illustrates the structure of the statistical testing plan. First, the co-primary endpoints will be evaluated for non-inferiority by comparing each two-sided 95% CI to the appropriate non-inferiority margin. Conditional on both co-primary endpoints achieving non-inferiority (i.e., passing the gatekeeper), the family of MACE and the principal secondary endpoints will be formally tested for superiority using the widely known Holm-Bonferroni procedure [Holm, 1979]. The procedure will be conducted based on a family-wise Type I error rate set at the one-sided 2.5% level. Details of the Holm-Bonferroni procedure will be fully described in the RAP.

Section 9.4.5 describes the planned interim analysis for the assessment of MACE futility. While this analysis will have a small impact on reducing the study-wise Type I error rate, there are no plans to adjust the alpha level used for end-of-study analyses. There are no prospectively defined plans to stop this study early for benefit.

Figure 2 Multiplicity controlled statistical testing plan

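### Adding Day 1 ferritin and TSAT to the IV iron ANCOVA would be a free precision gain; the model is valid without them

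*Protocol*

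**What the plan says.** The endpoint is listed in Section 3 as "Average monthly IV iron dose (mg)/subject to Week 52". It stands with MACE and two MACE-based composites, so the superiority family has four members. Section 9.4.3 tests this family by Holm-Bonferroni once both co-primaries have passed: "The procedure will be conducted based on a family-wise Type I error rate set at the one-sided 2.5% level".

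Section 9.4.2.1 gives the model as an ANCOVA "including factors for baseline dose, treatment and the prognostic randomization stratification factors". Section 4.1 identifies those factors: "Dialysis type and region are stratification factors considered to be potentially prognostically important". The covariate list is stated outright and is not deferred to the Reporting and Analysis Plan (RAP). Section 9.4.4, on covariates and subgroups, leaves room for the RAP to define more covariates but commits to none.

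Three other places bear on the point:

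- Section 6.11.1 applies from Day 1 to the end of treatment. "Iron therapy will be administered if ferritin is" at or below 100 ng/mL and/or TSAT is at or below 20%. Iron must stop if ferritin exceeds 800 ng/mL with TSAT above 20%, or if TSAT exceeds 40%. The investigator chooses route and dose.
- Section 5.2 excludes ferritin at or below 100 ng/mL and TSAT at or below 20%, at screening only. It sets no upper limit.
- Table 7 schedules "Ferritin, total iron, UIBC" at screening and on Day 1, and a footnote makes all Day 1 assessments pre-dose. Table 10 lists TSAT among the central laboratory parameters.

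**The concern.** A subject's iron status at the start should carry information about how much IV iron follows. Someone who starts above a stop limit cannot be given iron at first, and someone who starts close to a start threshold is more likely to need it soon. If this information is not already carried by baseline iron dose, dialysis type and region, it stays in the error term. The standard error of the treatment difference is then larger than it need be, in a test that may have to pass at one-sided 0.00625. Only power is at stake.

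**Working it through.** **No plan figure to reproduce.** The protocol states no SD, effect size or power for IV iron, so the size below rests on an assumed range.

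**1. Are the Day 1 values plausibly prognostic?**
- The iron criteria begin on Day 1, so the Day 1 values are the first to which they apply.
- The entry limits apply at screening (Week -8). Section 7 places Day 1 seven to nine weeks later, so a subject can be at or below a start threshold by then.
- Entry has no upper limit, so a subject can be randomized above a stop limit.
- Between the limits, Day 1 values show how far a subject starts from each one.

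**2. Is the test valid without them?** Allocation is 1:1 and central, with about 3000 subjects. In a linear ANCOVA under randomization, omitting a baseline covariate affects precision only. A null simulation illustrates this: 4000 trials of 3000 subjects, dose driven by baseline dose, ferritin, TSAT, dialysis type and region, all inputs assumed.

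| Model | Mean difference (mg) | Mean SE | Type I error at 0.025 | Type I error at 0.00625 |
|---|---|---|---|---|
| Without ferritin and TSAT | 0.05 | 2.994 | 0.022 | 0.0045 |
| With ferritin and TSAT | 0.08 | 2.873 | 0.019 | 0.0043 |

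Neither model shows bias or inflation. The SE ratio is 2.873/2.994 = 0.960, a 4% reduction. That figure reflects the simulation's inputs and is not evidence about this trial.

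**3. How much precision could be gained?** Let R² be the share of residual variance that the two covariates explain beyond baseline dose, dialysis type and region. Assume 0.05 to 0.10.
- SE multiplier = √(1 − R²): √0.95 = 0.975 (2.5% lower) and √0.90 = 0.949 (5.1% lower).
- Equivalent sample size = 1/(1 − R²): 1/0.95 = 1.053 (5% more subjects) and 1/0.90 = 1.111 (11% more).

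**4. What would that mean for power?** The first Holm step is 0.025/4 = 0.00625, with z = 2.498. Suppose the test has 80% power there without the covariates (z = 0.842). The standardized effect is then 2.498 + 0.842, or 3.339 before rounding the parts.
- R² = 0.05: 3.339/0.975 − 2.498 = 0.928, power 0.823.
- R² = 0.10: 3.339/0.949 − 2.498 = 1.022, power 0.847.

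**The case against.** The strongest reply is that nothing here is wrong. The model has the same structure as the hemoglobin co-primary ANCOVA in Section 9.4.1.2: treatment, the baseline of the endpoint, dialysis type and region. A short prespecified list is conventional, error control is intact, and the RAP, which is not at hand, may add covariates. All of that stands, which is why this is offered as an improvement. The general permission in Section 9.4.4 does not, however, change the model that Section 9.4.2.1 states.

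The reply also says that the gain may be small. On-study values govern iron use, and between the thresholds the protocol neither requires nor forbids iron. Route and dose follow local practice, the criteria cover iron by any route while the endpoint counts IV iron only, and baseline dose and region already capture part of local practice. This also stands, and it leaves the size of the gain open.

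A reader might infer that baseline ferritin and TSAT decide who receives iron. Section 6.11.1 does not support that, because the values measured during treatment and the investigator's choices decide. *Likely prognostic* is as far as the text goes.

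A reader might also infer that the baseline dose term is weak because it covers only four weeks. That window, in Appendix 2, belongs to an exploratory endpoint on reduced IV iron use. Section 9.4.2.1 gives no window for its own baseline dose.

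**Conclusion.** The IV iron ANCOVA is valid as written and can be made more precise at almost no cost. It might be tempting to read the omission as a threat to a multiplicity-controlled test. It is not one: randomization protects the estimate, and the type I error is not inflated with or without the covariates.

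The size of the gain is unknown from the documents. The 5% to 10% of residual variance and the 80% starting power are both assumptions. Under them the power gain is about 2 to 5 percentage points at one-sided 0.00625, a level that binds only if IV iron has the smallest of the four p-values; later Holm steps are less strict. If the covariates explain less than assumed, the gain shrinks towards nothing, and with about 3000 subjects two extra terms cost next to nothing in degrees of freedom. This is worth doing but not essential.

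**What to change.** In Section 9.4.2.1, and correspondingly in the RAP, add Day 1 log ferritin and Day 1 TSAT as continuous covariates alongside baseline IV iron dose, dialysis type and region. Use the screening value where Day 1 is missing. State that on-study ferritin and TSAT are never used, because treatment can affect them and adjusting for them could distort the comparison. Fix this before unblinding. If the RAP already includes these terms, confirming that is enough.

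The cost is a short text change that settles the functional form and the missing-data rule. No new data, visits or samples are needed.
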